6.2 FIDELITY

6.2.1 INTERVENTIONIST TRAINING AND TRACKING

The dieticians are RDs with specific expertise in caring for patients with liver disease. Study staff will be trained on how to provide tailored feedback on physical activity (step count goals). They had demonstrated proficiency in following standard procedures.

6.3 MEASURES TO MINIMIZE BIAS: RANDOMIZATION AND BLINDING

Participants in this trial will be randomized to either the intervention arm (tailored physical activity and nutritional counseling) or a wait-list control arm that receives usual care for 6 months, after which they will receive the intervention (for 6 months). Neither participants nor interventionists are blinded to study arm.

6.4 STUDY INTERVENTION/EXPERIMENTAL MANIPULATION ADHERENCE

Adherence will be assessed by the following:

-Completion of all study visits and data collection elements

-Percentage of days with valid FitBit data (>300 steps per day as defined in behavioral health literature). Step count data will be assessed weekly for each participant.

6.5 CONCOMITANT THERAPY

Participants can continue any treatments that are not listed as part of the exclusion criteria for this study.

7 STUDY INTERVENTION/EXPERIMENTAL MANIPULATION DISCONTINUATION AND PARTICIPANT DISCONTINUATION/WITHDRAWAL

7.1 DISCONTINUATION OF STUDY INTERVENTION/EXPERIMENTAL MANIPULATION

Discontinuation from study intervention does not mean discontinuation from the study, and remaining study procedures should be completed as indicated by the study protocol. If a clinically significant finding is identified (including, but not limited to changes from baseline) after enrollment, the investigator or qualified designee will determine if any change in participant management is needed. Any new clinically relevant finding will be reported as an adverse event (AE).

The minimum data to be collected at the time of study intervention discontinuation will include the following:

- Weight and anthropometrics, laboratory studies, HRQOL and VCTE if possible.
- Download of all available Fitbit data

7.2 PARTICIPANT DISCONTINUATION/WITHDRAWAL FROM THE STUDY

Participants are free to withdraw from participation in the study at any time upon request. An investigator may discontinue or withdraw a participant from the study for the following reasons:

- Pregnancy
- If any clinical adverse event (AE), laboratory abnormality, or other medical condition or situation occurs such that continued participation in the study would not be in the best interest of the participant
- Disease progression which requires discontinuation of the study intervention

- If the participant meets an exclusion criterion (either newly developed or not previously recognized) that precludes further study participation
- Participant unable to receive study intervention for 30 days/4 weeks
- Start of new therapy/program that is not allowed while enrolled in this study

The reason for participant discontinuation or withdrawal from the study will be recorded on the appropriate CRF. Subjects who sign the informed consent form and are randomized but do not receive the study intervention may be replaced. Subjects who sign the informed consent form, and are randomized and receive the study intervention, and subsequently withdraw, or are withdrawn or discontinued from the study, will not be replaced.

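### Section 7.2 permits withdrawal from the study after 30 days without the intervention; before month 6 that ground exists only in Arm I, and nothing secures the 6-month CAP of those withdrawn

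*Combined protocol and SAP*

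**What the plan says.** Section 7.1 separates leaving the intervention from leaving the study: "Discontinuation from study intervention does not mean discontinuation from the study, and remaining study procedures should be completed". When the intervention stops, it asks for a minimum dataset at that moment: "Weight and anthropometrics, laboratory studies, HRQOL and VCTE if possible", plus the FitBit data.

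Section 7.2 concerns leaving the study. Its list opens with "An investigator may discontinue or withdraw a participant from the study for the following reasons" and includes "Participant unable to receive study intervention for 30 days/4 weeks", "Disease progression which requires discontinuation of the study intervention", "Start of new therapy/program that is not allowed while enrolled in this study" and "If the participant meets an exclusion criterion (either newly developed or not previously recognized) that precludes further study participation". For those withdrawn it adds one data requirement: "The reason for participant discontinuation or withdrawal from the study will be recorded on the appropriate CRF".

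Four other places bear on this:

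- Section 4.1 and the caption to Table 2 in section 1.3 start the controls' intervention at month 6, after Visit 2.
- Section 3 sets the primary endpoint as a CAP reduction of at least 5% at 6 months.
- Section 6.3 states that participants and interventionists are not blinded.
- Section 9.3.2 assigns participants without follow-up imaging to a modified intention-to-treat analysis and adds a completer analysis. It does not say whether a missing CAP is dropped or counted as non-response.

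**The concern.** The 30-day ground turns a problem with delivering the intervention into a reason to end outcome collection. Up to Visit 2, only Arm I has an intervention to miss. The decision is discretionary, no criteria guide it, and it is made by staff who know the arm.

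If the trial is read as a between-arm comparison at 6 months, primary outcomes can be lost through a rule that works on one side of the randomisation only. Participants who cannot take part for a month may well differ in response from those who can. Outcomes never collected cannot be recovered at analysis.

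**Working it through.** **Step 1: does the ground apply to one arm only before the endpoint?** The endpoint is measured at Visit 2 (day 168). Controls begin the intervention after that visit. Table 2 does mark FitBit provision and the dietician assessment at Visit 1 for the control arm, but the FitBit row is labelled for the intervention arm, and the caption and section 4.1 both place the controls' intervention after Visit 2. So before the 6-month CAP only Arm I can meet the 30-day ground.

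**Step 2: does any text secure the CAP of those withdrawn?**

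- Section 7.1 protects people who stop the intervention but remain in the study. Its minimum dataset is taken when the intervention stops, and the scan is subject to feasibility, so it is not the month-6 CAP.
- Section 7.2 asks only for the reason.
- Section 7.3 covers missed visits and lost contact.
- Section 9.3.2 says how missing imaging is analysed, not how it is obtained.

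Nothing closes the gap for participants withdrawn under 7.2.

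**Step 3: how large could the effect be?** The plan has no figure to reproduce here: it gives no response rate, no rate of withdrawal on this ground and no named test. Section 9.2 gives only dropout of up to 20% from all causes, which is 0.20 × 60 = 12 per arm. The following is therefore an illustration on assumed inputs.

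- Design: two-proportion comparison between arms, 60 per arm (section 4.1), two-sided alpha 0.05 (section 9.3.1).
- Assumed: no true effect and 30% responders in each arm.
- Assumed: a share w = 5% or 10% of Arm I withdrawn (3 or 6 of 60), with response rate r = 15% or 30% among them.

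Observed Arm I rate if those withdrawn are dropped: (0.30 − w·r)/(1 − w).

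Observed Arm I rate if they are counted as non-responders: 0.30 − w·r.

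| r | w | Handling | Arm I rate | Shift (points) | Two-sided error |
|---|---|---|---|---|---|
| 15% | 5% | dropped | 0.2925/0.95 = 30.8% of 57 | +0.8 | 5.1% |
| 15% | 5% | non-response | 29.25% of 60 | −0.75 | 5.1% |
| 15% | 10% | dropped | 0.285/0.90 = 31.7% of 54 | +1.7 | 5.4% |
| 15% | 10% | non-response | 28.5% of 60 | −1.5 | 5.4% |
| 30% | 5% | dropped | 30.0% of 57 | 0 | 5.0% |
| 30% | 5% | non-response | 28.5% of 60 | −1.5 | 5.4% |
| 30% | 10% | dropped | 30.0% of 54 | 0 | 5.0% |
| 30% | 10% | non-response | 27.0% of 60 | −3.0 | 6.5% |

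The pooled standard error under the null, sqrt[p(1 − p)(1/n₁ + 1/60)], runs from 8.2 to 8.7 points. Error rates are normal approximations.

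As an extreme, if every withdrawn participant were a non-responder and all were dropped, the shifts would be 0.30/0.95 − 0.30 = +1.6 and 0.30/0.90 − 0.30 = +3.3 points, with error 5.4% and 6.7%. Counting missing CAP as non-response would bring both shifts to zero.

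**The case against.** The strongest reply is that the default is already right and the exposure slight. Section 7.1 keeps people in the study, 7.2 only permits withdrawal, and an investigator can follow both. That stands: a reader might infer that the sections contradict each other, but the permissive wording makes this a tension.

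The ground is also narrow. The intervention is a FitBit, e-mailed feedback, a dietician assessment and a phone call, so inability to receive it for a month should be uncommon. Low FitBit use does not by itself trigger withdrawal; section 6.1.1 has staff contact the participant. Withdrawing 3-6 of Arm I on this ground would use a quarter to a half of that arm's 12 anticipated dropouts, so the illustration is generous. All of this stands, and it limits the size of the point.

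The one-arm harm also depends on the analysis. Section 4.2 speaks of a pre-post analysis, and section 9.1 frames the primary hypothesis around those who complete the intervention. On those readings the ground can arise in either arm during its own intervention period. Section 3, however, sets the primary objective as a comparison with usual care, so the between-arm reading is live and the point holds for it.

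A reader might extend the argument to the disease-progression ground, whose wording also presupposes an intervention to discontinue. The documents do not support a real asymmetry in exposure there: a control who progresses can be withdrawn on the adverse-event or medical-condition ground, or for a newly developed exclusion such as decompensation.

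**Conclusion.** The point holds as a modest one. Section 7.2 allows study withdrawal on a ground that, before the 6-month CAP, exists in Arm I only, and no text secures the Visit 2 scan of those withdrawn. For a between-arm analysis, primary outcomes can be lost for a one-sided reason.

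Under the tabulated assumptions the difference shifts by 0 to 3 points in absolute size, and two-sided error lies between 5.0% and 6.5%. That is small against the standard error.

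A reader might infer that the rule favours the intervention. The documents do not support a direction: dropping poorer responders favours it, counting the withdrawn as non-responders goes against it, and dropping people who respond like the rest does neither. The case for change is that the remedy is cheap and lost outcomes cannot be retrieved.

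**What to change.** Amend section 7.2 so that three conditions may stop the intervention but do not by themselves end follow-up:

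- inability to receive the intervention for 30 days;
- disease progression requiring the intervention to stop;
- starting a disallowed programme.

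Still seek the Visit 2 scan and weight from these participants unless consent is withdrawn, the assessment is unsafe, or pregnancy intervenes. Include the data in the arm randomised in the between-arm 6-month analysis.

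Leave the adverse-event ground, the pregnancy rule (section 8.3.7) and exclusion criteria that genuinely preclude participation as they are. Exclusions 6 and 7 in section 5.2 concern weight-loss programmes and medication, so the amended text should say that starting one of these during the study falls under the programme ground.

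The cost is amendment wording and a few assessments already scheduled for all 120 participants; reasons for withdrawal are already recorded. The downside is that outcomes after a competing programme stay in the main analysis and may dilute the effect, so show a sensitivity analysis excluding them beside it.

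The change reduces missing CAP but does not remove it. Section 9.3.2's exclusion of randomised participants who never provided FitBit data is a separate matter that this amendment does not settle.

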12 NOVEMBER 2019

		p		nent	
OnCore Calendar Segment	Pre-Study	Consented OnStudy		OnTreatment	Off Study
Study Timeline	Pre-screening (Pre-consent)	Visit 1 Day 1	Visit 2 Day 168 ±7	Phone Call- Intervention Arm Day 252 ±14	Visit 3 Day 336 ±21
EMR Review Eligibility	х				
Informed Consent		х			
Demographics		х			
Clinical history		х			
Randomization		х			
Provide FitBit and Instruction to Intervention Arm		х	х		
Outcome Evaluation					
Vitals + Anthropometrics: blood pressure, height, weight, waist and hip circumference		х	х		х
Blood Work: ¹ hepatic panel, platelets, A1c, fasting insulin, glucose, lipid panel		х	х		х
6MWT		Х	х		х
Hand Grip Strength		х	х		х
Quality of Life Questionnaire ⁴		х	х		х
Physical Activity Survey (IPAQ) ⁴		х	х		х
Motivation to Change Questionnaire ⁴		х	Х		х
Dietary Survey ⁴		х	Х	х	х
Dietician Assessment ²		х			
VCTE ¹		х	Х		х
MRE1 ^{1,3}		х	Х		
Exit Interviews			Х		х
Adverse Events Reporting		х	Х	Х	х

Table 2. Arm II - wait list control; receives intervention after visit 2

¹Baseline results can be abstracted from medical record if performed within prior 6 months and <5% weight change since that time. Otherwise, VCTE will be performed +/- 14 days from enrollment. Hepatic panel and platelet count are standard of care measures. Remainder of imaging and laboratory data will be research costs. ²Can be done +/- 14 days from enrollment in person or via telephone

³ Only done in half of patients due to cost, determined by computer randomization with stratification according to liver disease stage (cirrhosis)

⁴ If not enough time during enrollment, participants will be sent a link via email to complete the surveys within 14 days from enrollment date.

EMR, electronic medical record; 6MWT, 6 minute walk test; IPAQ, International Physical activity Questionnaire; VCTE, vibration controlled transient elastography; MRE, magnetic resonance elastography

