4 STUDY DESIGN

4.1 OVERALL DESIGN

This randomized clinical pilot trial will compare a mobile technology-based lifestyle intervention to a waitlist control group receiving usual care for adult patients with NAFLD. The intervention will use FitBit to track and promote physical activity through tailored longitudinal feedback. Patient will also receive nutritional counseling with serial nutritional assessments. The primary endpoint will be change in amount of hepatic steatosis. Secondary outcomes include changes in weight and physical activity (assessed by trend in step counts). A wait-list control design will be applied. 60 Patients will be randomized to the intervention arm for 6 months and 60 to usual care (the wait-list control). Those initially randomized to the intervention arm will then transition to a 6-month post intervention monitoring period to assess maintenance of behavior change and sustainability of impact on outcomes of interest. Individuals initially randomized to usual care, will transition to the intervention at month 6 for a total of 6 months.

The intervention arm will receive tailored physical activity and nutritional counseling, and the waitlist control arm which will follow usual and customary care for NAFLD patients attending our Heptology clinic for 6 months and then receive the 6-month intervention.

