9.2 SAMPLE SIZE DETERMINATION

Sample size calculations will be made based on the total N for the cohort. Enrollment of 120 patients in the intervention should provide adequate power to assess for parameters associated with \geq 5% reduction in steatosis and weight loss using 80% power, alpha 0.05. We anticipate a dropout rate of up to 20%.

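### The replacement rule in Section 7.2 depends on having received the intervention, so it lets control losses before month 6 be replaced but not intervention-arm losses after the start

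*Combined protocol and SAP*

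**What the plan says.** Section 7.2 has two sentences on replacement. The first reads "Subjects who sign the informed consent form and are randomized but do not receive the study intervention may be replaced". The second covers people who consent "and are randomized and receive the study intervention, and subsequently withdraw, or are withdrawn or discontinued from the study, will not be replaced". Neither mentions the wait-list arm.

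The arms start the intervention at different times. Section 4.1 states: "Individuals initially randomized to usual care, will transition to the intervention at month 6 for a total of 6 months". The schedule in Section 1.3 is titled "Table 2. Arm II - wait list control; receives intervention after visit 2", and the Section 1.2 schema and Section 6.3 agree. For the intervention arm, Table 1 in Section 1.3 marks both randomisation and FitBit provision at Visit 1, Day 1, and Section 6.1.1 gives a FitBit to all 60.

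The primary endpoint in Section 3 is at 6 months. On masking, Section 6.3 says "Neither participants nor interventionists are blinded to study arm". On losses, Section 9.2 says "We anticipate a dropout rate of up to 20" percent.

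**The concern.** A rule of this kind is neutral when both arms begin treatment on Day 1. Here it is not. For the whole randomised comparison period, a control is by design someone who has been randomised and has not received the intervention. A control who withdraws at any time before month 6 therefore fits the sentence that allows replacement. An intervention participant who starts and then withdraws at the same time fits the sentence that forbids it.

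At stake is the comparability of the arms at month 6. Replacement decisions would be taken after allocation is known. If a replacement takes the vacated control place, staff also know that person's arm before enrolling them. If the person replaced is then left out of the analysis, the control arm is partly made up of people chosen after the event, while the intervention arm carries its losses.

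**Working it through.** **Who may be replaced, by arm and timing (Section 7.2 read with Sections 1.2, 1.3, 4.1, 6.1.1 and 6.3)**

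| Situation | Intervention arm | Wait-list arm |
|---|---|---|
| Leaves before receiving anything | may be replaced | may be replaced |
| Leaves later, before month 6 | not replaced | may be replaced |
| Leaves after starting the intervention at month 6 | does not arise | not replaced |

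The asymmetry is the middle row. Section 7.2 does not define receipt. If it means the FitBit handover, the intervention arm's replaceable window closes on Day 1. On a more demanding reading that waits for the nutritional assessment (Section 6.1.1, within 2 weeks of enrolment), it closes at about 2 weeks. For controls it stays open to Visit 2, Day 168, that is 168 / 7 = 24 weeks.

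**The plan's own figure.** The total of 120 in Section 9.2 cannot be reproduced, because no control responder rate, effect size or standard deviation is given. The finding does not depend on it. The dropout arithmetic is simple: 120 × 0.8 = 96 completers, or 60 × 0.8 = 48 per arm.

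**Upper bound on the imbalance.** Inputs are 60 per arm (Section 4.1) and dropout d up to 20% (Section 9.2). Assumptions: all dropout is before month 6, intervention losses occur after the start, every permitted replacement is made, each takes a control place, and replacements drop out at the same rate.

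- Intervention completers: 60(1 − d)
- Control completers after one round: 60(1 − d) + 60d(1 − d)
- Controls randomised to reach 60 completers: 60 / (1 − d)

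| d | Intervention completers | Control completers, one round | Controls randomised for 60 completers |
|---|---|---|---|
| 5% | 57 | 59.9 | 63.2 |
| 10% | 54 | 59.4 | 66.7 |
| 15% | 51 | 58.7 | 70.6 |
| 20% | 48 | 57.6 | 75 |

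At 20%: 60 × 0.20 = 12 losses per arm, and 48 + 12 × 0.8 = 57.6, about 58, from 72 controls randomised. The 10% row also shows the case where half of the 20% falls before month 6.

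If the 12 replacements were instead randomised afresh 1:1, 6 would go to each arm and each would expect 48 + 6 × 0.8 = 52.8 completers. The imbalance needs replacements to be placed in the control arm, and the plan does not say whether they would be.

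**Whether imbalance becomes bias.** As an illustration, assume no true effect, the same responder rate p among completers in both arms, and non-completers counted as non-responders (the plan specifies no such rule).

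- Intervention: 48p / 60 = 0.8p.
- Control, replaced people left out, 60 completers: 60p / 60 = p.
- Control, all 75 randomised kept: 60p / 75 = 0.8p.

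With replaced controls left out, p = 0.2 gives 16% against 20%, p = 0.3 gives 24% against 30%, and p = 0.5 gives 40% against 50%. That is a spurious gap of 4 to 10 points against the intervention. With all randomised controls kept, the gap is zero.

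**The case against.** Several points on the other side are fair.

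- **Replacement is optional.** The wording permits it and does not require it. This stands, and it is why the figures are upper bounds.
- **The premise is not wholly clean.** Table 2 in Section 1.3 marks FitBit provision and the dietician assessment at Visit 1 for the wait-list arm, and Section 6.1.1 describes usual care beneath the Study Intervention(s) heading. However, the FitBit row is labelled as being for the intervention arm, the marks conflict with the table's own title and with Sections 1.2, 4.1 and 6.3, and Section 6.1.1 contrasts the intervention with usual care. These points show ambiguity that needs reconciling; they do not remove the asymmetry.
- **Unequal numbers are not bias.** This stands. Bias depends on allocation and analysis rules that the plan does not give.

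A reader might also infer more than the documents support:

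- *That month 6 would be 60 controls against 48.* This ignores dropout among the replacements. One round gives about 58, and 60 completers needs 75 controls randomised.
- *That no intervention-arm loss can be replaced.* Non-starters can be.
- *That a late replacement must overrun the study.* Adding 6 months to the synopsis's 13-month participation gives 19, above the 18-month study duration. The schedule gives 168 + 336 = 504 days, about 16.6 months, or 175 + 357 = 532 days, about 17.5 months, at the upper visit windows. An overrun is not established.
- *That replacement conceals feasibility failures.* Section 7.2 records the reason for every withdrawal, and Section 6.4 counts visit completion as adherence.
- *That a control who declines the crossover loses their month-6 data.* Nothing says so, and Section 7.1 separates stopping the intervention from leaving the study.

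**Conclusion.** The concern holds. As written, Section 7.2 is arm-dependent throughout the randomised period: it permits replacement of any control who withdraws before the month-6 endpoint and, in the intervention arm, only of people who never started. In an open-label trial this allows selective topping-up of one arm after allocation.

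Under the assumptions above, the largest effect on numbers after one round is 48 intervention against about 58 control completers, compared with 48 against 48 without replacement. The size, and even the existence, of bias cannot be determined, because the plan is silent on how replacements are allocated and on whether replaced participants are analysed. Section 9.3.2 adds to the doubt. It drops randomised people who never supplied FitBit data, and a control who leaves before month 6 would ordinarily have none. It does not say whether the exclusion is meant to apply to controls.

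This should be fixed. Given an optional rule with unknown impact in a pilot, the documents do not support calling it more serious than that.

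**What to change.** Replace the two sentences in Section 7.2 with: *No participant is replaced after randomisation in either arm. People who consent but are not randomised are screen failures (Section 5.4) and may be replaced.* An arm-neutral replacement criterion would also remove the asymmetry, but it would still need allocation and analysis rules; barring replacement is simpler.

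Three changes go with it:

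- State that all randomised participants stay in their assigned arm for the month-6 comparison, including controls who decline the crossover, and amend the FitBit-data exclusion in Section 9.3.2 so that it does not contradict this.
- Report non-starters and losses before month 6 by arm.
- Reconcile the Visit 1 FitBit and dietician marks in Table 2 with that table's title.

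The cost is a short amendment to Sections 7.2, 9.3.2 and 1.3. Final numbers are not topped up, but Section 9.2 already anticipates 20% dropout. For scale, under assumed responder rates of 20% and 45%, power is about 75% with 48 against 48 and 80% with 60 controls against 48. Under 30% and 55% it is about 70% and 75%. That is a loss of about 5 points relative to the fullest topping-up.
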